6.1.2. Adverse Event Lists for olaparib

Adverse events observed with olaparib are detailed in the Investigator's Brochure (IB). As of October 2, 2013, >2100 patients have received olaparib in doses ranging from 10mg daily to 600mg BID, either as monotherapy or in combination with other chemotherapy agents (liposomal doxorubicin, cisplatin, dacarbazine, gemcitabine, gemcitabine+cisplatin, carboplatin, carboplatin+paclitaxel, paclitaxel, topotecan, irinotecan, or bevacizumab). Preliminary unvalidated safety data are available for several studies and are detailed in the IB.

Aes considered to be associated with administration of olaparib included laboratory findings and/or clinical diagnoses of anemia (generally mild to moderate, CTC grade 1 or 2), neutropenia (predominantly mild to moderate, CTC grade 1 or 2), thrombocytopenia (generally mild to moderate, CTC grade 1 or 2; sometimes severe, CTC grade 3 or 4), nausea and vomiting (generally mild to moderate, CTC grade 1 or 2, intermittent and manageable on continued treatment), and fatigue (generally intermittent, of mild to moderate intensity CTC grade 1 or 2). Pneumonitis events with no consistent clinical pattern have been reported in a small number of patients. Rare hematologic malignancies, including myelodysplasia, have also been reported. Please see the table below, titled "Summary of Adverse Drug Reactions from Completed Clinical Trials of Olaparib," for a summary of the adverse drug reactions from completed trials of olaparib.

In the first clinical study in man, a total of 98 patients in the study were evaluable for safety. As expected in patients with advanced cancer, all of the patients experienced at least one adverse event. In total, 81 patients (82.7%) experienced at least one adverse event that the investigator attributed to study medication. Most of the Aes were mild to moderate in intensity. The number of patients with CTC grade ≥ 3 events attributed to study medication was low (24 patients, 21.4%) and increased with increasing dose. The observed Aes in each system are detailed below.

- **Gastrointestinal Disorders**
The most common gastrointestinal Aes were nausea (56 of 98 patients, 57%) and vomiting (44 of 98 patients, 45%). Most were of mild to moderate intensity (CTC grade 1 or 2), intermittent, and manageable on continued treatment. Abdominal pain (24 of 98 patients, 24.5%), constipation (18 of 98 patients, 18.4%), and diarrhea (25 of 98 patients, 25.5%) were also observed.
- **General Disorders**
The most common general AE reported was fatigue, which was observed in 52 patients (53%). Cases of fatigue were generally intermittent and of mild to moderate intensity (CTC grade 1 or 2). Other Aes included pyrexia (10 patients, 10%) and peripheral edema (16 patients, 16%).
- **Cardiac Disorders**

29 patients reported mild (CTC grade 1), asymptomatic tachycardia. None of these cases required treatment, and all events were considered to be unrelated to study drug.

- **Nervous System Disorders**

The most common nervous system Aes reported were headache (15%), dizziness (11%), and dysgeusia (13%). Other reported Aes included somnolence, attention or mental impairment, cognitive disorder, dizziness, depression, and memory impairment.

- **Hematologic Disorders**

Laboratory findings and/or clinical diagnoses of anemia (generally mild to moderate, CTC grade 1 or 2), neutropenia (predominantly mild to moderate, CTC grade 1 or 2), and thrombocytopenia (generally mild to moderate, CTC grade 1 or 2, sometimes severe) were observed. The incidence of anemia was 26%, neutropenia was 1%, and thrombocytopenia was 5%. A few cases of myelodysplasia have been reported on studies including olaparib. Additionally, data from study D0810C00002 have demonstrated increases in MCV in approximately 30% of patients, especially in those receiving greater than 6 cycles of treatment, mild and moderate in intensity, and asymptomatic in nature. No clinical consequences have been associated with this finding.

MDS/AML have been reported in <1% of patients exposed to olaparib. The cases were typical of secondary MDS/therapy-related AML. The duration of therapy with olaparib in patients who developed secondary MDS/AML varied from <6 months to >2 years. All patients had potential contributing factors for the development of MDS/AML, having received extensive previous chemotherapy with platinum agents. Many had also received other DNA damaging agents.

New primary malignancies have been reported in a small number of patients. There were other contributing factors/potential alternative explanations for the development of the new primary malignancy in all cases.

Pneumonitis events have been reported in <1% of patients receiving olaparib. The reports of pneumonitis had no consistent clinical pattern and were confounded by a number of pre-disposing factors (cancer and/or metastases in lungs, underlying pulmonary disease, smoking history, and/or previous chemotherapy and radiotherapy).

6.2. **Dose Modifications/Delays**

In the phase 1 and phase 1-T components of this study, doses of cediranib and olaparib will be administered at the same dose level throughout a cycle if no DLTs occur. In cycle 1, patients experiencing non-hematologic Grade 2 Aes (or Grade 3 fatigue or hypertension) may have treatment held for up to 7 days for toxicity management. Treatment may then be resumed at the same dose level. Inability to take at least 75% of the planned dose of cediranib and olaparib in Cycle 1 due to drug-related toxicity is considered a DLT. If any individual patient develops a DLT, treatment for this patient will be stopped. If the toxicity is not resolved within 14 days, the patient will be removed from the study. Patients who experienced a DLT whose toxicity has

resolved to baseline or Grade 1 and whose therapy has been discontinued for less than 14 days may resume therapy at the previous (next lower) dose level if necessary. For patients who experience a DLT in the first cycle of the first cohort (cediranib 20mg daily and olaparib 100mg BID) whose toxicity has resolved to baseline or Grade 1 and whose therapy has been discontinued for less than 14 days, the dose may be reduced to cediranib 15mg daily and olaparib 100mg BID. During the DLT assessment period, both drugs must be held if there is an indication for either drug to be held.

For patients experiencing non-hematologic Grade 2 Aes (or Grade 3 fatigue or hypertension) in cycles 2 or greater, treatment may be held for up to 14 days for toxicity management if necessary. The treating physician may decide to hold treatment to ensure patient safety when grading and/or attribution is unclear. Patients whose treatment has been held for ≤ 7 days may then resume treatment at the same dose level. If treatment is held for > 7 days, please see Section 6.3.1 regarding dose modifications. For patients in the phase 1 and 1-T portions of the study in cycles 2 and beyond, dose modifications/delays should be managed as per Section 6.3.1. Tables for cediranib and olaparib dosing levels are provided in Sections 6.2.1 and 6.2.2.

In the phase 2 component of this study, dose modifications, and general management of Aes will be outlined as in Section 6.3.1. Dose modifications and delays for specific toxicities of hypertension, proteinuria, decrease in LVEF, diarrhea, fever and neutropenia, thyroid toxicities, and RPLS will be as further outlined in specific subsections in Section 6.3.

6.2.1. Table for Cediranib Dose Modification*

Dose Level	Cediranib
-2	15mg daily
-1	20mg daily
1	30mg daily

- * Presuming patients are being dosed at the maximum Phase 1 dose level of cediranib 30mg daily or being dosed as the starting phase 2 dose level of cediranib 30mg daily. Patients who are being treated at a different dose level on the Phase 1 or Phase 1-T portions of this trial may be dose-reduced per this table but may not be dose-escalated except as detailed in Section 5.

6.2.2. Tables for Olaparib Dose Modification

Phase I:

Dose Level	Olaparib (capsule)
-2	100mg twice daily
-1	200mg twice daily
1*	400mg twice daily

- * This dose level is applicable only for patients who were dosed at the maximum Phase 1 dose level of olaparib 400mg twice daily. Patients who are being treated at a different dose level on the Phase 1 portion of this trial may be dose-reduced per this table but may not be dose-escalated except as detailed in Section 5.

Phase I-TA:

Dose Level	Olaparib (tablet)
-2	100mg twice daily
-1	150mg twice daily
1	200mg twice daily
2	250mg twice daily
3	300mg twice daily

- * Patients may be dose-reduced per this table but may not be dose-escalated except as detailed in Section 5.

Phase I-TB:

Dose Level	Olaparib (tablet)
-3	150mg twice daily
-2	200mg twice daily
-1	250mg twice daily
1	300mg twice daily

- * Patients may be dose-reduced per this table but may not be dose-escalated except as detailed in Section 5.

Phase II:

For patients receiving olaparib **monotherapy**:

Dose Level	Olaparib (capsule)
-2	100mg twice daily
-1	200mg twice daily
1	400mg twice daily

For patients receiving olaparib and cediranib **combination therapy**:

Dose Level	Olaparib (capsule)
-2	100mg twice daily
-1	150mg twice daily
1	200mg twice daily

6.3. Toxicity Management

The management of general adverse events not otherwise specified will be as per the table in Section 6.3.1. Management of specific toxicities, including hypertension, proteinuria, decreased in LVEF, diarrhea, fever and neutropenia, thyroid toxicities, and RPLS will be as further outlined in specific subsections in Section 6.3.

6.3.1. Dose Modifications and Management of Cediranib and Olaparib Toxicities

General Management of Adverse Events (Non-Hematologic)	
Observation	Action
AE resolves promptly with supportive care	Maintain dose level
Any grade 2 non-hematologic AE or grade 3 fatigue related to cediranib or olaparib that persists despite maximal support.	Hold study drug(s) ¹ for up to 14 days until toxicity resolves to ≤ grade 1. ³ Treatment may be restarted at one dose level lower for the drug(s) causing the toxicity, as per the dose reduction levels in Sections 6.2.1 and 6.2.2, at the treating investigator's discretion. The overall PI of the study should be informed regarding all dose modifications. Patients whose toxicity has not resolved after 14 days will be removed from study.
Any ≥ grade 3 non-hematologic (excluding grade 3 fatigue or hypertension or easily correctable asymptomatic grade 3 laboratory abnormalities)	Hold study drug(s) ¹ for up to 14 days until toxicity resolves to ≤ grade 1. ³ Treatment may be restarted at one dose level lower for the drug(s) causing the toxicity, as per the dose reduction levels in Sections 6.2.1 and 6.2.2, at the treating investigator's discretion. The overall PI of the study should be informed regarding all dose modifications.
1. Grade 3 or 4 non-hematologic AE related to cediranib and olaparib combination that does not resolve to grade 0-2 within 14 days despite maximum supportive care after treating patient at the lowest reduced dose level. ² 2. Grade 3 or 4 non-hematologic AE related to cediranib/olaparib lasting > 14 days despite maximum supportive care and treatment being held.	Remove patient from study.

- 1 For patients receiving both cediranib and olaparib after the DLT assessment period has completed in the Phase 1 or Phase 1-T or for patients enrolled to the cediranib/olaparib arm in the Phase 2 -- if the observed AE is specifically attributed to only one of the drugs, that drug may be held while the patient continues to receive the drug not associated with the observed AE. The time a given drug is held should not exceed 14 days.
- 2 Excluding hypertension, see below 6.3.2
- 3 For thromboembolic events, treatment may be resumed at the discretion of the investigator once patient is asymptomatic. For weight loss events, treatment may be resumed at the discretion of the investigator once weight has stabilized.

Dose Modification and Management of Hematologic Adverse Events	
Observation	Action
Absolute neutrophil count \geq 1000/mcL AND Platelets \geq 75,000/mcL AND Hemoglobin \geq 8 mg/dL	Maintain dose level
Absolute neutrophil count < 1000/mcL OR Platelets < 75,000/mcL OR Hemoglobin < 8 mg/dL	Hold treatment for up to 14 days until absolute neutrophil count \geq 1000/mcL, platelets \geq 75,000/mcL, and hemoglobin \geq 8 mg/dL. Treatment may be restarted at one dose level lower for the drug(s) causing the toxicity, as per the dose reduction levels in Sections 6.2.1 and 6.2.2, at the treating investigator's discretion. The overall PI of the study should be informed regarding all dose modifications. Patients whose counts have not recovered to absolute neutrophil count \geq 1000/mcL, platelets \geq 75,000/mcL, and hemoglobin \geq 8 mg/dL after 14 days should be removed from study.
Grade 4 hematologic AE related to cediranib or olaparib that does not resolve to absolute neutrophil count \geq 1000/mcL, platelets \geq 75,000/mcL, and hemoglobin \geq 8 mg/dL despite maximum supportive care after 14 days.	Remove patient from study.

For AEs that are unrelated to the study drugs, study drug may be held for up to 14 days at the discretion of the treating investigator. Drug holds of greater than 14 days for unrelated AEs where the patient is experiencing ongoing clinical benefit may be considered after discussion with the overall PI.

Patients in the dual therapy arm, experiencing ongoing clinical benefit, who experience a related AE where continuation of one of the drugs is considered, in the judgment of the treating

investigator AND overall PI, to be potentially life-threatening or with the potential for long-term harm to the patient, may be allowed to continue on the unrelated drug after discussion with the overall PI.

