1. OBJECTIVES

1.1. Study Design

This is a Phase I/II trial of the combination of cediranib and olaparib in the treatment of recurrent ovarian, fallopian tube, or peritoneal cancer or in recurrent triple-negative breast cancer to define the safe dose of this combination, followed by a randomized two-arm Phase II study comparing the combination of cediranib and olaparib at the recommended Phase 2 dose (RP2D) as determined in the Phase I portion of the study compared to the control arm of olaparib alone in patients with recurrent platinum-sensitive papillary-serous or endometrioid ovarian, fallopian tube, or peritoneal cancer. A total of up to 148 patients are planned for study enrollment, with up to 28 patients in the phase I dose escalation portion, up to 90 patients in the Phase II randomized portion, and up to 30 patients in the phase I (tablet) dose escalation portion.

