- Patients may not have had a prior PARP-inhibitor in the recurrent or metastatic setting. Prior treatment with BSI-201 is allowed.
- Patients may not have had a prior anti-angiogenic agent in the recurrent or metastatic setting.

For Phase II Portion:

- Prior chemotherapy must have included a first-line platinum-based regimen with or without intravenous consolidation chemotherapy.
- Prior hormonal-based therapy for ovarian, primary peritoneal serous, or fallopian tube cancer is acceptable.
- Patients may not have previously received a PARP-inhibitor. Prior treatment with BSI-201 is allowed.
- Patients may not have had a prior anti-angiogenic agent in the recurrent setting.
- Patients may have received up to 1 non-platinum-based line of therapy in the recurrent setting.
- Patients may have received an unlimited number of platinum-based therapies in the recurrent setting.
- Patients should have platinum-sensitive disease, where platinum-sensitive disease is defined as having had a > 6 month interval since last receiving platinum therapy prior to disease recurrence. Patients must have had a prior response while on the platinum-containing regimen and cannot have experienced disease progression while receiving platinum.

Subjects may begin cediranib and olaparib at least 3 weeks after their last dose of chemotherapy or hormonal therapy, assuming they are otherwise eligible.

- 3.1.4.** Age \geq 18 years. Because no dosing or adverse event data are currently available on the use of cediranib or olaparib in participants < 18 years of age, children are excluded from this study but will be eligible for future pediatric trials.
- 3.1.5.** Estimated life expectancy of greater than 6 months.
- 3.1.6.** ECOG performance status 0 or 1 (Karnofsky > 60%, see Appendix A).
- 3.1.7.** Participants must have adequate organ and marrow function as defined below:
- Absolute neutrophil count \geq 1,500/mcL
 - Platelets \geq 100,000/mcL
 - Hemoglobin > 9 g/dL
 - For patients enrolled to the Phase 1-T portion of the protocol, the Hemoglobin should be \geq 10 g/dL
 - Total bilirubin within 1.5 times the upper limit of normal institutional limits
 - AST (SGOT)/ALT (SGPT) \leq 2.5 \times institutional upper limit of normal
 - Creatinine \leq the institutional upper limit of normal or creatinine clearance \geq 60 mL/min/1.73 m² for subjects with creatinine levels above institutional normal

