5.1. Pre-treatment Criteria

5.1.1. Screening Visit: Patients must meet criteria at screening as outlined in Section 3.1.

5.1.2. Hematologic Parameters for treatment:

Absolute Neutrophil Count:

- Cycle 1, Day 1: $\geq 1500/\text{mm}^3$
- Cycles 2 and Beyond, Day 1: $\geq 1000/\text{mm}^3$

For Phase 1-T patients:

- Hemoglobin:
 - Cycle 1, Day 1: $\geq 10\text{g/dL}$
 - Cycles 2 and beyond, Day 1: Per Table in Section 6.3.1
- Platelets:

- Cycle 1, Day 1: $\geq 100,000/\text{mL}$
- Cycles 2 and beyond, Day 1: Per Table in Section 6.3.1

5.1.3. All Cycles, Day 1: Patients must have all of the following:

- Adequate blood pressure control as detailed in Section 6.3.2.
- Serum creatinine $\leq 1.5 \times$ the institutional upper limit of normal
- Liver function test $\leq 2.5 \times$ upper limit of normal.
- ECOG performance status of 0 or 1.
- No evidence of life-threatening medical problems.

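### The hemoglobin limit in the Section 6.3.1 hematologic table is printed as 8 mg/dL in all five places; as written, low hemoglobin can never trigger a hold, dose reduction or removal

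*Combined protocol and SAP*

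**What the plan says.** The second table in Section 6.3.1 sets the action to take on neutrophils, platelets and hemoglobin. Its hold trigger reads "Absolute neutrophil count < 1000/mcL OR Platelets < 75,000/mcL OR Hemoglobin < 8 mg/dL". The hemoglobin figure of 8 mg/dL appears five times: in the row that keeps the dose unchanged, in the hold trigger, in the recovery needed to restart, in the removal rule after 14 days without recovery, and in the row on unresolved Grade 4 events.

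Other sections make this the working rule during treatment:

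- For Phase II, Section 6.2 says that "dose modifications, and general management of Aes will be outlined as in Section 6.3.1".
- For Phase 1 and Phase 1-T, Section 6.2 says that "in cycles 2 and beyond, dose modifications/delays should be managed as per Section 6.3.1".
- For Phase 1-T hemoglobin and platelets, Section 5.1.2 says "Cycles 2 and beyond, Day 1: Per Table in Section 6.3.1".

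Elsewhere hemoglobin is in g/dL. Section 3.1.7 requires "Hemoglobin > 9 g/dL" at entry, and at least 10 g/dL for Phase 1-T. Section 5.1.2 repeats the 10 g/dL minimum for Phase 1-T on Cycle 1 Day 1.

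**The concern.** The table decides when drug is stopped, restarted, reduced or withdrawn for low blood counts. With the printed unit, its hemoglobin condition separates no one: every living patient is above 8 mg/dL.

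Hemoglobin matters for these drugs. Section 2.2.2 names bone marrow as the target organ of olaparib toxicity. The olaparib risk list in Section 6.1.1 puts anemia in the category above 20%, and Section 6.1.2 reports 26% in the first-in-human study, generally Grade 1 or 2. Section 5.4 bars erythropoiesis-stimulating agents during treatment, which leaves more of the management to dose holds and reductions.

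There is also no correct number to fall back on in Phase II. The on-treatment hemoglobin check in Section 5.1.2 is for Phase 1-T only and points back to this table. Section 5.1.3, which applies on Day 1 of every cycle, lists no hemoglobin limit.

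**Working it through.** No sample size, power or error rate is involved. The check is a count, a unit conversion and a literal reading of each row.

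**Inputs**

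- Section 6.3.1 hematologic table: hemoglobin limit 8 mg/dL.
- Section 3.1.7: entry above 9 g/dL, or at least 10 g/dL for Phase 1-T.
- Section 5.1.2: at least 10 g/dL on Cycle 1 Day 1, Phase 1-T only.
- Section 1.1: up to 28 patients in Phase 1, 90 in Phase II and 30 in Phase 1-T.
- Conversion: 1 g/dL = 1,000 mg/dL.

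**Count.** One entry in the maintain row, one in the hold trigger, two in the hold row's action text (restart and 14-day removal) and one in the Grade 4 row: 1 + 1 + 2 + 1 = 5. All five read mg/dL.

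**Conversion**

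- Printed limit: 8 / 1,000 = 0.008 g/dL.
- Intended limit: 8 × 1,000 = 8,000 mg/dL, so the factor is 8,000 / 8 = 1,000.
- Entry limits on the printed scale: 9,000 and 10,000 mg/dL, which are 9,000 / 8 = 1,125 and 10,000 / 8 = 1,250 times the printed limit.
- A patient at 6 g/dL (my illustration): 6,000 mg/dL, or 6,000 / 8 = 750 times the printed limit.

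**Literal reading, with neutrophils at or above 1,000/mcL and platelets at or above 75,000/mcL**

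| Entry | Hemoglobin condition as printed | Result at 6 g/dL | Result if the unit were g/dL |
|---|---|---|---|
| Maintain dose | at least 8 mg/dL | met: dose unchanged | not met |
| Hold trigger | below 8 mg/dL | not met: no hold | met: hold |
| Recovery to restart | at least 8 mg/dL | already met | not met |
| Removal at 14 days | not back to 8 mg/dL | never applies | applies if still below 8 g/dL |
| Unresolved Grade 4 event | not back to 8 mg/dL | never applies to hemoglobin | applies if Grade 4, drug-related and still below 8 g/dL |

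**Plausibility of the correction.** 8 g/dL is 9 − 8 = 1 g/dL below the general entry limit and 10 − 8 = 2 g/dL below the Phase 1-T entry limit, a sensible place for a hold rule.

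**Reach.** Phase II: up to 90 patients from the start of treatment. Phase 1 and 1-T: 28 + 30 = 58 from Cycle 2. Together 90 + 58 = 148, the planned maximum.

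**Extraction fault?** Unlikely. The unit is the same in all five entries, the neutrophil and platelet units in those rows are usable, and g/dL came through correctly in Sections 3.1.7 and 5.1.2.

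**The case against.** The strongest reply is that this is a slip that corrects itself. A limit of 0.008 g/dL is physiologically impossible, the entry criteria show the intended scale, and any oncologist will read 8 g/dL. Other safeguards do not depend on the unit:

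- Section 5.1.3 requires ECOG 0 or 1 and no life-threatening medical problem on Day 1 of each cycle.
- Section 5.5 ends treatment for unacceptable adverse events or at the investigator's judgment.
- The Section 9.2 calendar has a blood count before each cycle and on Day 15 of Cycles 1 and 2.
- The monitoring board reviews toxicity every six months (Section 12.2).
- In Cycle 1 of the dose-escalation parts, Grade 4 hematologic toxicity is dose-limiting whatever this table says (Section 5.3).

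Dose reduction on restart is discretionary in any case. The documents show no case report form limit or edit check built from the table. The figure of 148 is an enrollment ceiling: only patients whose hemoglobin falls below 8 g/dL would meet the rule, and by this 2019 version many may already be off treatment.

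Most of this stands as a limit on the practical harm. It does not remove the error. None of the safeguards gives a numeric hemoglobin limit, which is what the table is for. The written rule is also the standard for compliance: Section 12.3 has data monitored for adherence to the protocol, and Appendix G, Section 8.1 counts any departure from its procedures as a deviation. On the printed text, continuing full dose at 6 g/dL complies, and holding at 7 g/dL is not what the table calls for. That a data-system limit might copy the printed unit is a possibility to check; the documents do not show that it happened.

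**Conclusion.** The concern holds. All five hemoglobin entries in the hematologic table are wrong by a factor of 1,000, and as printed the hemoglobin part of the hold, reduce and remove rule cannot act. The neutrophil and platelet parts still work. This should be fixed because it is a wrong threshold in the operative on-treatment safety rule, even though clinicians will probably read it correctly.

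The conclusion assumes that 8 g/dL was meant, which the entry limits support. The documents give no rate of hemoglobin below 8 g/dL, so no number of affected patients is claimed. There is no claimed effect on the dose-limiting toxicity or maximum tolerated dose decisions, the sample size, or the progression-free survival analysis.

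**What to change.** In the Section 6.3.1 hematologic table, change mg/dL to g/dL in all five hemoglobin entries. Keep the value 8. Confirm that any hemoglobin limits in case report forms, edit checks or monitoring guides are in g/dL.

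While the text is open, compare the Phase 1-T Cycle 1 Day 1 platelet unit in Section 5.1.2 with the source document. It reads per mL in the text available for review, which may be an extraction fault; if it is really printed so, change it to per mcL as in Section 3.1.7. This is a check only and not part of the finding.

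The cost is a wording correction in the next amendment, with no added patients, visits or tests.
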